8.2.2 Analysis of Secondary and Exploratory endpoints

Descriptive analyses will be conducted to summarize subject characteristics and detect potential selection bias as a result of missing data or dropout.

All subjects who sign informed consent will be included in safety analyses and in calculation of the rate of AEs, regardless of whether and how much study drug was received. Safety and tolerability will be assessed by clinical review of all relevant parameters including AEs, laboratory tests, and vital signs. Safety summaries will be provided for both cohorts. Immune-related adverse events (irAEs, as defined in Section 9), are prespecified events of interest. These events will be summarized in separate tables from other AEs by toxicity grade and will include the counts, percentages, and 95% CI. AEs (specific terms as well as system organ class terms) that are not pre-specified as events of interest will be summarized with descriptive statistics (counts, percentage, mean, standard deviation, etc).

Progression-free survival (PFS) and overall survival (OS) will be estimated using the Kaplan-Meier product-limit method, with subjects censored at their last known date alive. Standard error for the Kaplan-Meier estimate will be calculated according to the formula of Peto, et al (*Br J Cancer* 1977) and a two-sided 95% confidence intervals for the median PFS and median OS, respectively, will also be calculated.

Comparisons of PFS and OS in subjects on Cohort A (nonsurgical) vs. PFS and OS in subjects on Cohort B (neoadjuvant therapy) will be exploratory in nature, as the study is not adequately powered for these comparisons. Log-rank tests will be used to explore differences in PFS/OS between these two groups.

For analysis of correlative data, variable distributions will be presented graphically and descriptively at each time point; if needed, appropriate transformations will be performed. Paired t-tests will be used to assess change from pre- to post-treatment for exploratory endpoints that are normally distributed. Wilcoxon signed-rank tests will be used to assess change from pre- to post-treatment for exploratory endpoints that are not normally distributed. Multiple comparison adjustment using false discovery rate (FDR) will be used. The sample size of 16 subjects in the surgical arm of the study (Cohort B), with N=8 per sub-arm provides 85% power with one-sided alpha of 0.05 to detect the difference between the null hypothesis of a CD8+ tumor-infiltrating lymphocyte score of 1 and the alternative hypothesis of a CD8+ tumor-infiltrating lymphocyte score of 1.85. These numbers are based on the pre- and post- CD8+ tumor-infiltrating lymphocyte scoring system (scored 0 to 3, least to most CD8+ T cell infiltration) used in our prior CAR T cell trial in recurrent GBM (O'Rourke, *Sci Transl Med* 2017), which is one of the few immunotherapies shown to increase tumor T cell infiltration in this disease. In that study,

pre-CAR T cell GBM specimens had a mean score of 1 (standard deviation 0.1) and post-CAR T cell GBM specimens had a mean score of 1.85 (standard deviation 0.80).

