3.1.1. Screening Phase

Subjects will be recruited from the Medical Oncology, Radiation Oncology, and Neurosurgery practices at the University of Pennsylvania Health System. The treating physician will determine

if the patient is a potential research candidate. The treating physician will approach and inform the patient about the study, thereby initiating the informed consent process. If the patient expresses interest in the study, the treating physician will contact a qualified member of the research team in the Neurosurgery Clinical Research Division at the University of Pennsylvania and request availability for enrollment. A sub-investigator will continue the formal consent process. This person will explain the requirements of the study and provide a copy of the Informed Consent Form. The person obtaining consent will state the volunteer nature of research and advise the subject to take sufficient time to discuss the study before making her decision to sign the informed consent document. If a decision to participate is made, the informed consent form is signed after which screening procedures will be performed. Subject eligibility will be evaluated based upon the criteria outlined in the protocol. After eligibility is established, a subject study number will be issued. Eligibility is confirmed with a clinically-licensed study Investigator. All members of the research team will have successfully completed patient oriented research training.

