As long as the subject has not withdrawn his/her consent, the non-treated (replaced) subject is followed for safety follow-up per [Table 10](#) (see [Section 6](#)) and all safety-related data collected for the subject is included in analysis of the study's secondary safety/tolerability endpoints. However, the subject is not included in the primary endpoint efficacy analysis or in analysis of secondary efficacy endpoints (see [Section 8, Statistical Plan](#)). In addition, if the replaced subject was enrolled during the safety run-in phase, that subject will not be counted for purposes of determining whether the pre-specified safety criteria (see [Section 3.1; General Design](#)) have been met during the safety run-in phase to allow for successful completion of the safety run-in phase.

Subject replacement occurs up to and no more than 7 times for Cohort A [i.e., up to 23 subjects can be enrolled to obtain 16 subjects who receive both of the study drugs at the same dose and schedule AND SRS and are therefore evaluable for the primary endpoint].

Cohort B: Any subject who is enrolled onto Cohort B of the study but meets one of the following criteria is replaced by enrollment of a new subject onto Cohort B:

- The subject is enrolled, but does not receive either of the systemic agents (INCMGA00012, INCAGN01876)
- The subject is enrolled, but does not receive SRS (surgical subarm #1 only)
- The subject is enrolled, but does not undergo surgery

As long as the subject has not withdrawn his/her consent, the non-treated (replaced) subject is followed for safety follow-up per [Table 10](#) (see [Section 6](#)) and all safety-related data collected for the subject is included in analysis of secondary study endpoints.

Subject replacement occurs up to and no more than 10 times for Cohort B [i.e., up to 26 subjects can be enrolled to obtain 16 subjects who receive neoadjuvant therapy AND undergo surgery, with 8 patients assigned to each of the 2 sub-arms]. Subjects who need to be replaced in Cohort B, will be replaced by a subject enrolled onto the same sub-arm that the replaced subject was previously on.

Replaced subjects will be followed for safety only. These subjects will not be included in efficacy endpoint analyses, and they will not have tumor tissue available for correlative endpoint analyses.

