3.3. Duration of Individual Subject Study Participation

After signing the ICF, screening procedures commence. Each enrolled subject begins study treatment. Treatment continues until the subject meets any one or more of the criteria for study drug discontinuation (see [Section 5.7; Study Drug Discontinuation Criteria](#)). When a subject discontinues study drug but has not withdrawn consent, the subject enters the follow-up period. Subjects are taken off study if any of the following criteria apply:

- Lost to follow-up
- Withdrawal of consent
- Death
- Sponsor decides to terminate the study

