6.2. Subject Withdrawal from the Study

Subjects may withdraw consent for the study at any time for any reason without impact to their care. In addition, a subject may be withdrawn by the investigator or the sponsor if enrollment in the study is inappropriate, lack of adherence to the intervention or study procedures or visit schedules, the study plan is violated, or for administrative and/or other safety reasons. It is documented whether or not each subject completes the clinical study. If the subject actively withdraws consent for collection of follow-up data (i.e., subsequent anticancer treatments, safety follow-up, and survival), then no additional data collection occurs; however, all subjects are informed of the option to discontinue treatment and/or study assessments but allow collection of information in the follow-up period of the study. In the event that the latter occurs, the end-of-treatment (EOT) visit should be conducted (see **Table 8** and **Table 9** for EOT visit procedures). Thereafter, the subject will return for follow-up visits for safety and disease/survival status, with procedures as outlined above in **Table 10**.

If a subject withdraws from the study and has not yet received a dose of study drug, that subject is replaced according to the procedure outlined in **Section 3.2; Replacement of Subjects**.

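### Section 8.2.2 counts every consenter, treated or not, in the irAE denominator, so irAE rates are understated if any consenter is never dosed

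*Combined protocol and SAP*

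**What the plan says.** Section 8.2.2 sets the safety population: "All subjects who sign informed consent will be included in safety analyses and in calculation of the rate of AEs", and this holds "regardless of whether and how much study drug was received". The same paragraph makes irAEs the prespecified events of interest, tabulated by grade in summaries that "will include the counts, percentages, and 95% CI". It promises safety summaries for both cohorts. It gives irAEs no denominator of their own, and no treated-only safety set is defined elsewhere in the document.

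Other sections bear on who is in that population:

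- **3.1.1:** consent comes before screening; "the informed consent form is signed after which screening procedures will be performed". A subject number follows only once eligibility is established.
- **6.2:** "If a subject withdraws from the study and has not yet received a dose of study drug, that subject is replaced".
- **3.2:** "the non-treated (replaced) subject is followed for safety follow-up", and "all safety-related data collected for the subject is included in analysis of" the secondary safety endpoints.
- **3.3:** "Each enrolled subject begins study treatment".
- **9.1.2:** an irAE is defined as an event associated with drug exposure.
- **9.2:** AE collection starts at consent.

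**The concern.** For an event that is defined by exposure, the numerator and denominator should come from the same exposed group. Here they do not. A consenter who never receives drug adds one to the denominator and, under 9.1.2, cannot add to the numerator. The error has one direction: it makes the regimen look safer.

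Safety and tolerability is a secondary objective, and irAEs are the only adverse events for which 8.2.2 plans a confidence interval. Section 5.8.1 expects that adding GITR agonism to PD-1 inhibition could make immune-related toxicity more frequent or more severe, and dilution works against seeing that. The comparison data in 1.3.1.2 and 1.3.2.2 are on exposed subjects (199 on INCMGA00012 monotherapy, 221 who had at least one dose of INCAGN01876), so rates on an all-consenter base would not be like for like.

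The same dilution would affect any treatment-related rate computed on this set, although 8.2.2 plans none. All-cause AE rates could move in either direction.

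**Working it through.** The plan states no irAE rate, interval or safety N, so there is no figure of its own to reproduce.

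**Inputs.** From the documents: 16 subjects per cohort, 32 in total. Assumed, because the documents do not give them: the number of subjects with an irAE (x), the number of never-treated consenters (U), and the interval method, which 8.2.2 does not name. Clopper-Pearson is used, with Wilson as a check.

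**Formulas.**

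- Reported rate = x/(T+U) = (x/T) × T/(T+U).
- Clopper-Pearson 95% limits for x out of n: lower = 2.5% quantile of Beta(x, n−x+1); upper = 97.5% quantile of Beta(x+1, n−x). For x = 0 the lower limit is 0.

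**Within Cohort A (T = 16).** The shrinkage factor is 16/17 = 0.94 for U = 1 and 16/18 = 0.89 for U = 2.

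| Subjects with irAE | Treated only (n = 16) | U = 1 (n = 17) | U = 2 (n = 18) |
|---|---|---|---|
| 0, upper limit | 20.6% | 19.5% | 18.5% |
| 4 | 25.0% (7.3–52.4) | 23.5% (6.8–49.9) | 22.2% (6.4–47.6) |
| 8 | 50.0% (24.7–75.3) | 47.1% (23.0–72.2) | 44.4% (21.5–69.2) |

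For 4 events the estimate drops by 25.0 − 23.5 = 1.5 points, or 25.0 − 22.2 = 2.8 points, against an interval 52.4 − 7.3 = 45.1 points wide.

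**Overall rate, if one is reported and screen failures are counted (T = 32, x = 8).**

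| Denominator | Rate | 95% CI |
|---|---|---|
| 32 treated | 25.0% | 11.5–43.4 |
| 36 (U = 4) | 22.2% | 10.1–39.2 |
| 40 (U = 8) | 20.0% | 9.1–35.6 |

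**Direction.** For every T from 5 to 49, U from 1 to 19 and x from 1 to T, the percentage and both Clopper-Pearson limits fall. For x = 0 only the upper limit falls. Wilson intervals move the same way: 8/32 gives 13.3–42.1 and 8/40 gives 10.5–34.8; 4/16 gives 10.2–49.5 and 4/18 gives 9.0–45.2.

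**Width.** The interval narrows at low to moderate rates but widens once the rate in treated subjects reaches about 75% (12 events of 16 with U = 1 or 2; 24 of 32 with U = 4; 25 of 32 with U = 8). For example, 28/32 has width 25.5 points and 28/36 has 29.0. The constant feature is the downward shift, not spurious precision.

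**The case against.** The strongest reply is that U is probably very small where it counts. Section 3.3 has every enrolled subject start treatment, and the schedule gives drug before SRS or surgery. Section 8.2.2 most naturally describes summaries by cohort; no pooled rate is specified, and screen failures belong to no cohort. The larger figures therefore need both an overall rate that is not clearly planned and an assumed number of screen failures counted in it.

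Nor does 3.2 show that many unexposed people enter. It calls every replaced subject non-treated, yet four of its seven Cohort A criteria concern subjects who did receive study drug, and those belong in the denominator. The replacement caps (7 in Cohort A, 10 in Cohort B) are therefore not estimates of U.

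Further, every diluted estimate shown lies inside the treated-only interval. No test or decision uses the irAE interval. Counts stand beside the percentages, so a reader who is also told the number treated can recompute. Counting from consent also fits the AE collection window in 9.2.

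All of this stands as a limit on size. It does not rescue the rule. The text expressly admits people with no exposure, 3.1.1 and 6.2 foresee such people, and 8.2.2 does not say where screen failures go in the by-cohort tables. Collecting events from consent is sound, but it does not require an all-consenter denominator for an exposure-defined event.

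**Conclusion.** The concern holds. As written, 8.2.2 understates the irAE percentage among treated subjects whenever at least one irAE occurs and at least one consenter is never dosed. With no irAE, only the upper limit is too low. If every consenter is treated there is no bias.

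The likely effect within a cohort is one to three percentage points under the assumed counts (4 events, one or two undosed subjects). An overall rate that included four to eight screen failures would lose about three to five points at 8 events in 32. These sizes rest on assumed U, event counts and interval method; the direction does not. This is a safety-reporting correction that should be made, and it leaves the primary analysis and the run-in rules untouched.

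**What to change.** In 8.2.2, define the denominator for irAE percentages and their 95% intervals, and for any treatment-related rate that is reported, as all subjects who received any amount of either study drug or any SRS fraction, presented by cohort. Keep dosed subjects who are later replaced. Since drug is scheduled before SRS, this set should equal the drug-exposed set; a definition by study drug alone would serve equally well and matches 9.1.2 more closely. List events before first treatment, and events in never-treated consenters, separately. Naming the interval method in the same place would be useful.

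The cost is one or two sentences. No new data are needed: 5.4 has drug dispensing recorded and 9.2 already captures AE start dates. The only downside is that irAE percentages may come out somewhat less favourable.

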2.2. Study Endpoints

2.2.1. Primary Endpoint:

- Objective radiographic response (ORR), as measured by modified Response Assessment in Neuro-Oncology (RANO) criteria

2.2.2. Secondary Endpoints:

- Safety and tolerability will be assessed by monitoring frequency, duration, and severity of adverse events (AEs) through physical examinations, by evaluating changes in vital signs, and through clinical laboratory evaluations.
- OS, defined as the time from date of enrollment until death from any cause
- PFS, defined as the time from date of enrollment until the earliest date of disease progression (as determined by modified RANO criteria) or death due to any cause

2.2.3 Exploratory Endpoints:

- Comparison of the following immunocorrelative assays in subjects treated with INCMGA00012 + INCAGN01876, with or without SRS:
 - Multiplex immunohistochemistry on tumor tissue for CD4/8 T cell infiltration, Foxp3+ Treg infiltration, and PD-1/PD-L1 expression
 - Tumor cell and immune cell GITR expression by a validated immunohistochemistry stain
 - Flow cytometry/mass cytometry in tumor tissue and peripheral blood for T cell and monocyte phenotyping
 - RNA-Seq on tumor tissue for PD-1/PD-L1 and GITR expression, T cell- and interferon- γ -related gene expression, and cell-cycle-related gene expression
 - T cell receptor sequencing in tumor tissue and peripheral blood for assessment of TCR clonal diversity
- Association between the above tumor tissue and peripheral blood-based markers of immune activation, tumor genetic mutations, and clinical outcomes of OS, PFS, and ORR
- PK parameters for INCAGN01876 in patients with glioblastoma
- Detection of anti-drug antibodies (ADA) against INCAGN01876

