3.1.3.2. Disease Status Follow-Up

Subjects who discontinue study drug treatment but who have not yet met criteria for disease progression are assessed by radiologic imaging to monitor disease status. These assessments occur every 12 weeks (\pm 14 days). The imaging assessments occur at the study site if the subject continues to receive care at the University of Pennsylvania; otherwise, research staff will obtain subject's outside radiology reports and outside physician notes to determine disease status. If possible, the original images from radiology scans will also be obtained for formal radiologic interpretation by University of Pennsylvania Neuroradiology.

Every effort should be made to collect information regarding disease status until:

- The start of new antineoplastic therapy.
- Disease progression.
- Death.
- Termination of the study
- 5 years after removal from protocol therapy

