3.1.3.3. Survival Follow-Up

Subjects are contacted by telephone, e-mail, or visit every 12 weeks (+/-14 days) from the 12-week safety follow-up visit to capture survival status until death, withdrawal of consent, termination of the study or 5 years after removal from protocol therapy, whichever occurs first. Public records/databases are searched if contact with the subject is lost.

For participants who are thought to be lost to follow-up, at least 3 documented attempts should be made to contact the participant before the participant is deemed lost to follow-up.

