Adverse Event / Unanticipated Problems Assessment (Section 7)	X	X		X	X	X		X	X	X	X	X		X
INCMGA00012 Administration (Section 5)		X††				X			X		X			
INCAGN01876 Administration (Section 5)		X††				X		X	X	X	X	X		
MRI brain (tumor assessment by mRANO criteria) (Section 7)	X												X*	X†††
SRS planning** (Section 5)	X													
SRS delivery** (Section 5)			X											
Surgical Resection; tissue for correlatives (Section 7)				X										

* MRI scan should be performed within 7 days prior to the cycle start (and ideally within 3 days prior). Adjustments to this 7-day window are allowable per the treating physician’s discretion; however restaging scans MUST BE performed and reviewed before the subsequent cycle’s dose may be initiated

**SRS delivery: Total 24 Gy delivered over 3 consecutive days (8 Gy per day). Subjects may receive 3 fractions every other day (non-consecutively) for logistical reasons relating to COVID-19. Must start between 3 and 7 days after first dose of study drugs

*** PK samples for INCAGN01876 collected pre-dose and at end of infusion on Cycle 1 Day 1 and Cycle 3 Day 15. All other PK draws for INCAGN01876 are pre-dose.

† After the first 2 cycles, PK samples for INCAGN01876 are drawn only on Cycle 3 Day 15, Cycle 4 Day 1, Cycle 4 Day 15, and then only on day 15 of each cycle starting with Cycle 5

†† For the neoadjuvant dose(s) of study drugs INCMGA00012 and INCAGN01876, the subject will be assigned to receive the combination of INCMGA00012 and INCAGN01876, or the combination of INCMGA00012 and INCAGN01876 plus SRS. After surgery ALL subjects will resume the combination of both INCMGA00012 and INCAGN01876

††† MRI and mRANO assessment at EOT are only necessary if this has not already been performed within 28 days of the EOT visit
§ EOT visit occurs within 14 days from when the subject is taken off study

Table 10: Schedule of study procedures, FOLLOW-UP			
Procedure	Safety visit	Safety follow-up	Disease Status and Survival
	30 d after EOT (+/- 7 d)	12 W (+/-14 d) after EOT	Q12W after EOT (+/- 14d)
Karnofsky Performance Status (Section 7)	X		
Targeted Physical Assessment (Section 7)	X		
Vital Signs: BP, HR, RR, weight (Section 7)	X		
Prior/Concomitant Medications (Section 7)	X	X	
Clinical Laboratory Evaluation (CBC, CMP, Mag, Phos, LDH) (Section 7)	X		
Urinalysis (Section 7)	X		
Clinical laboratory Evaluation – endocrine (TSH, T4) (Section 7)	X		
Urine Pregnancy Test (Section 7)	X		

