Adverse Event / Unanticipated Problems Assessment (Section 7)	X	X*	
MRI brain (tumor assessment) (Section 7)			X
Subject Vital Status (Collection of survival information every 3 months until death, lost to follow-up, or withdrawal of study consent)			X

* Only immune related Adverse Events are to be collected at the 12-week safety follow- up timepoint (see sections 1.3.1.3 and 1.3.2.3).

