7.7.2. Response/Progression Categories

The following definitions for disease response and progression will be used according to the following MRI and clinical criteria:

Complete Response (CR): Requires **all** of the following:

1. Disappearance of all enhancing measurable and non-measurable disease sustained for at least 4 weeks. In the absence of a confirming scan at least 4 weeks later, this scan will be considered only stable disease.
2. No new lesions
3. Stable or improved non-enhancing (T2/FLAIR) lesions
4. Patients must be off corticosteroids (or on physiologic replacement doses only).
5. Stable or improved clinical assessments

Partial Response (PR): Requires **all** of the following:

1. $\geq 50\%$ decrease in sum of products of perpendicular diameters of all measurable enhancing lesions compared with baseline, sustained for at least 4 weeks. In the absence of a confirming scan at least 4 weeks later, this scan will be considered only stable disease.
2. No progression of non-measurable disease
3. No new lesions
4. Stable or improved non-enhancing (T2/FLAIR) lesions
5. Steroid dose should be the same or lower compared with baseline scan.
6. Stable or improved clinical assessments.

Progressive Disease (PD) is defined by *any* of the following:

1. $\geq 25\%$ increase in sum of products of perpendicular diameters of enhancing lesions compared with the smallest tumor measurement [obtained either at baseline (if no decrease) or best response], on stable or increasing doses of corticosteroids.
2. Any new enhancing measurable lesion
3. Clear clinical deterioration not attributable to other causes apart from tumor (e.g. seizures, medication adverse effects, therapy complications, stroke, infection) or attributable to changes in steroid dose. The definition of clinical deterioration is left to the discretion of the investigator.
4. Clear progression of non-measurable disease
5. Failure to return for evaluation as a result of death or deteriorating condition.

Stable Disease (SD): Requires **all** of the following:

1. Does not qualify for CR, PR, or PD as defined above.
2. Stable non-enhancing (T2/FLAIR) lesions on same or lower dose of corticosteroids compared with baseline scan
3. Clinically stable

The response and progression criteria to be used in this study are summarized in **Table 13**:

Table 13. Summary of the RANO response Criteria:

Criterion	CR	PR	SD	PD
T1w CE	None	≥ 50 % ↓	<50%↓ but <25 %↑	≥25% ↑*

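### Section 8.2.2 censors PFS at the OS date, so a living subject whose disease assessments ended before progression counts as progression-free up to last survival contact

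*Combined protocol and SAP*

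**What the plan says.** - **Censoring.** Section 8.2.2 estimates PFS and OS together by Kaplan-Meier, "with subjects censored at their last known date alive". No other section sets a different date for PFS; the synopsis says only that the curves will be produced.
- **Event.** Section 2.2.2 defines PFS as time from enrollment to the "earliest date of disease progression (as determined by modified RANO criteria) or death due to any cause".
- **End of disease assessment.** Section 3.1.3.2 schedules 12-weekly imaging after study drug is stopped without progression. It lists the points at which collection may end, and "The start of new antineoplastic therapy" is one of them, separate from progression and death.
- **End of survival contact.** Section 3.1.3.3 continues contact every 12 weeks by telephone, e-mail or visit "to capture survival status until death, withdrawal of consent, termination of the study or 5 years after removal from protocol therapy". It adds: "Public records/databases are searched if contact with the subject is lost". Table 10 describes the same item as "Collection of survival information every 3 months until death, lost to follow-up, or withdrawal of study consent". None of this requires a scan.
- **What narrows the gap.** Section 7.7.2 counts as progression "Failure to return for evaluation as a result of death or deteriorating condition", and also clear clinical deterioration. Table 10 places MRI and vital status in the same 12-weekly column.

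**The concern.** Being known alive does not show that a subject is progression-free. Section 3.1.3.2 lets disease assessment end at new therapy, and Section 3.1.3.3 has no such stop. The protocol itself therefore creates a period in which vital status is known and progression status is not. Under Section 8.2.2 a subject without recorded progression who is alive at cutoff stays in the PFS risk set throughout that period.

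The outputs at stake are the secondary PFS curve, its median and confidence interval, and the log-rank comparison of Cohorts A and B, which Section 8.2.2 itself calls exploratory and underpowered. No decision rule uses PFS. An analyst who notices the problem late would have to follow an unsuitable rule or depart from the plan after seeing data.

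**Working it through.** **No plan figure to reproduce.** The documents give no target PFS, event count or power for PFS, and no share of subjects whose assessments stop before progression. What follows is an illustration under assumptions.

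**Direction.** Take a subject with last progression-free assessment at time L, alive and without recorded progression at last contact C > L. As written, censoring is at C; corrected, at L. All events, deaths included, stay where they are. Moving a censoring time from C back to L can only shrink the risk set at event times between L and C. Each Kaplan-Meier factor 1 − d/n then stays equal or falls. The written curve is therefore equal to or above the corrected one at every time.

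**Assumed inputs (none from the documents).** Median time to progression 3 months, so a = ln2/3 = 0.2310 per month. Median survival after progression 7 months, so b = ln2/7 = 0.0990. Assessment stops independently of progression at hazard h = a·s/(1 − s), where s is the share stopping before progression. Progression is seen when it happens, so the scan grid is ignored. Data cutoff is uniform over 12–30 months from enrollment.

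**Closed-form check, six months, s = 10%** (six-month PFS is used for illustration and is not a planned statistic). h = 0.2310/9 = 0.0257. True value: exp(−6a) = 25.0%. As written:

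S(t) = exp(−(a+h)t) + ∫₀ᵗ h·exp(−(a+h)u)·[a·exp(−b(t−u)) − b·exp(−a(t−u))]/(a−b) du

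At t = 6 the first term is exp(−1.540) = 0.214. The integral is [h/(a−b)]·(0.495 − 0.138) = 0.194 × 0.357 = 0.069. The sum is 0.284 to rounding, or 28.4%.

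**Large-sample simulation.** The corrected rule keeps deaths as events. The last column also drops deaths that occur after assessment stopped.

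| Share stopping | Quantity | As written | Corrected | Late deaths also dropped | True |
|---|---|---|---|---|---|
| 10% | median (months) | 3.14 | 3.10 | 3.00 | 3.00 |
| 10% | six-month PFS | 28.4% | 27.3% | 25.0% | 25.0% |
| 30% | median (months) | 3.64 | 3.43 | 3.00 | 3.00 |
| 30% | six-month PFS | 36.5% | 33.1% | 25.0% | 25.0% |

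The correction removes about a third of the excess: at 10%, (28.4 − 27.3)/(28.4 − 25.0) = 1.1/3.4 = 32%. The rest comes from deaths long after the last assessment, which Section 2.2.2 makes events. The share removed is about half with cutoff at 6–24 months and about a tenth at 24–42 months.

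**At N = 16, cutoff 12–30 months.** The censoring date changes for 3.4% or 9.6% of subjects, so 0.034 × 16 = 0.5 or 0.096 × 16 = 1.5 subjects. In 20,000 simulated trials the Kaplan-Meier median differs between the rules in about 0.2% (s = 10%) or 4.5% (s = 30%). The 95% sampling range of the median under the written rule at s = 10% is about 1.2 to 5.7 months.

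**Side effect of the correction.** With cutoff at 6–12 months and s = 30%, the corrected median is closer to the truth (3.14 against 3.65 as written, true 3.00). Near 12 months, however, the corrected curve gives about 2.3% against a true 6.4%. Subjects who stop assessment stay at risk afterwards only if they die, so the tail can fall too low.

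**The case against.** The best counter-argument is that few subjects are exposed. Section 3.1.3.2 asks for every effort and uses outside radiology reports and physician notes when care moves elsewhere. Section 7.7.2 turns deterioration, and non-return because of it, into progression. Restaging scans must be reviewed before the next cycle's dose, and MRI and vital status share a schedule after treatment ends. Subjects who die are PFS events under either wording. This stands. The documented exposed group is mainly subjects who stop drug without progression, start new therapy before progression, and are alive at cutoff. The 30% scenario has no documentary basis.

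A second objection concerns the remedy. Section 7.7.2 makes a time point non-evaluable when steroids change within two weeks of the MRI. A rule tied only to evaluable mRANO scans could therefore censor subjects just as steroid need rises, and it would leave the status of outside reports open. This also stands, and the wording below has to deal with both.

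Neither objection rescues the written rule. No section overrides it for PFS, and starting new therapy before progression is outside the deterioration criteria.

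A reader might infer that reported PFS will be heavily inflated. Such data can be constructed. Suppose 12 of 16 subjects progress (four at 1.8, four at 3.7, two at 5.5 and two at 7.4 months), and four have a last scan at 1.9 months and are alive at 12. Six-month PFS is then 6/16 = 37.5% as written, against 12/16 × 4/8 × 2/4 = 18.8% corrected. That pattern is hand-picked, the statistic is not planned, and the median is 3.7 months either way. It shows direction, not expected size.

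**Conclusion.** The sentence is wrong as written for PFS, and the point is minor. Relative to censoring at the last disease assessment with deaths kept, it can only raise the secondary PFS curve or leave it unchanged. The size cannot be determined from the documents. Under the assumed 3-month and 7-month medians, independent stopping in 10% of subjects and cutoff at 12–30 months, it is 0.04 months on the large-sample median, probably well below sampling error at N = 16. The primary ORR test does not depend on it.

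Two further readings are not supported. Late deaths are not miscounted against the plan, because Section 2.2.2 makes death from any cause a PFS event. Nor does the correction make PFS unbiased: it leaves the excess from late deaths in place, and with short follow-up it can push the tail below the truth.

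**What to change.** Split the sentence in Section 8.2.2:

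> OS: a subject not known to have died is censored at the last date known to be alive. PFS: a subject without documented progression or death is censored at the date of the last disease assessment documenting absence of progression, including outside imaging reports and notes used to determine disease status under 3.1.3.2, or at enrollment if there is none.

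Add a sentence stating how time points made non-evaluable by a steroid change under Section 7.7.2 are handled. Keep death from any cause as a PFS event, as in Section 2.2.2.

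Prespecify one sensitivity analysis that censors at the last such assessment before new antineoplastic therapy, or before a gap in assessments whose length is fixed in advance.

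**Costs.**
- The text edit is short, but PFS follow-up ends earlier for some subjects.
- The excess from late deaths remains, and the late part of the curve can fall too low when follow-up is short.
- Non-evaluable scans around steroid increases may make the censoring informative.
- The sensitivity analysis needs the start date of new therapy. Section 6.2 names subsequent anticancer treatment as follow-up data, but Table 10 has no row for it.
- The sensitivity analysis has no guaranteed direction and should not be the main analysis. If assessment stops at 80% of the time to progression and median survival after progression is 2 months, dropping deaths after stopping gives six-month PFS of 28.2% against 27.5% as written (10% stopping), or 36.1% against 32.5% (30%).
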